Eighty per cent (80%) of all 40 active procedure group subjects met the Positive Responder Rate compared with no (0%) placebo group subjects. Chi Square analysis found the differences between each of the 3 active procedure groups and the placebo group to be statistically significant, at p<0.0001.

ABC Global and Subscale Scores Across Study Duration: Mean change in each of the ABC Global Score and 5 Subscale Sores across study duration between procedure groups was evaluated through ANOVA analysis. Mean changes in scores for test group subjects decreased progressively and sizably across study duration including during a 4-week follow-up period during which time no procedures were administered, with the changes found to be statistically significant for each of the 3 active procedure groups (p<0.0001). Conversely, all scores were essentially unchanged across study duration for placebo group subjects and not statistically significant, at p>0.05.

CGI-S Scores: Change in CGI-S scores across study duration between procedure groups was evaluated. At baseline, all subjects (100%) in both procedure groups were rated in the top 3 severity of condition ratings of '5: Marked', '6: Severe' or '7: Amongst the most extreme of all patients with this condition'. CGI-S scores improved progressively and substantially across study duration for each of the 3 active procedure group subjects but not for placebo group subjects. By Week 8, all placebo group subjects (100%) retained a 5-7 CGI-S rating while only 35% of all 40 active procedure subjects retained a 5-7 CGS-S rating.

CGI-C Scores: Change in CGI-C scores across study duration between procedure groups was evaluated. CGI-C ratings for each of the 3 active procedure group subjects demonstrated continuous progressive improvement in symptom presentation across study duration. By Week 8, the presentation of symptoms and behaviors of autistic disorder for 85% of all 40 active procedure group subjects were reported as being 'Very Much Improved' or 'Much Improved' Conversely, there was essentially no change in CGI-C ratings across study duration for placebo group subjects.

6 Month Long-Term Follow-Up Evaluation: All 19 subjects originally randomized to the placebo subject group completed an additional 6-month post-procedure evaluation. Each of the outcome measures continued to demonstrate meaningful progressive improvement.

Adverse Events: No adverse event was reported for or by any subject throughout study duration.

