- 2) The fake (placebo) Erchonia® HLS is designed to have the same physical appearance as the actual Erchonia® HLS, including the appearance of any visible light output, and neither the active nor the placebo lasers put out any notable degree of heat or noise. Therefore, there are no distinguishing factors between the active and placebo lasers for subjects or investigators. Additional information on the design, application and proven ineffectiveness of the placebo HLS Laser Device to be used in this study is contained above on pages 10-11 of this protocol document under the section titled: PLACEBO DEVICE INFORMATION.
- 3) There will be two independent investigators interacting with subjects: (i) administration investigator: who will be responsible for administrating the study treatments; (ii) assessment investigator: who will be responsible for recording the study outcome measures. Only the administration investigator will be aware of whether a subject is assigned to Treatment Group A or B, although he or she will not be made aware of whether A or B corresponds to the true or fake laser. Neither the assessment investigator nor the subject will be aware of the subject's A/B Group assignment. In this way, the assessment investigator will not be able to form an association between A/B Treatment Group and active/sham device over the course of the study if a treatment effect is observed.

4) During the laser procedures, both the subject and the administration investigator will wear safety glasses that filter out the laser light spectrum. The administration investigator will wear KenTek Corporation KenTek C22-KMT-6101 light blue safety glasses and the subject will wear KenTek Corporation KGOG-6101 light blue Medium safety goggles. Additional information on this safety eyewear is contained above on pages 6-8 under the section titled: DEVICE SAFETY: RISK AND PREVENTION OF EYE INJURY.

TREATMENT GROUP RANDOMIZATION

Subject allocation to treatment group (A or B) will be via a randomized block design with varying block sizes of two, four and six subjects. In each block, one-half of the subjects will be randomly assigned to Group A and the other half will be randomly assigned to Group B.

Randomization will be attained using computer generation sequence methodology, ensuring that the randomization methodology and the generated allocation sequence is concealed from the investigator and subjects.

Concealment will be insured as follows:

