CAREGIVER SATISFACTION WITH STUDY OUTCOME

The subject's caregiver is asked to rate how satisfied he or she is with any change in their child's autism symptoms and behaviors overall following completion of the laser administration procedures with the Erchonia® HLS by using the 5-point Likert scale presented below to respond to the following question:

"Overall, how satisfied or dissatisfied are you with any change in your child's autism symptoms and behaviors overall following the study procedures with the study laser device?"

- Very Satisfied
- Somewhat Satisfied
- Neither Satisfied nor Dissatisfied
- Not Very Satisfied
- Not at All Satisfied

The **Spanish Translation** of the study Caregiver Satisfaction with Study Outcome assessment tool that will be administered in this study will be performed by Language Scientific, Inc. The translated document will be supported by a notarized Certification of Translation

BLINDING EFFICACY EVALUATION TOOLS

Caregiver Perceived Group Allocation and Rationale

The caregiver records whether he or she believes that their child received the study treatment with the true or fake Erchonia® HLS and records verbatim his or her reasoning or rationale for this perceived determination.

Assessment Investigator Perceived Subject Group Allocation and Rationale

The Assessment Investigator records whether he or she believes the subject to have received the study treatment with the true or fake Erchonia® HLS™ and records verbatim his or her reasoning or rationale for this perceived determination.

The **Spanish Translation** of the study Blinding Efficacy Evaluation assessment tools that will be administered in this study will be performed by Language Scientific, Inc. The translated documents will be supported by a notarized Certification of Translation.

STUDY PROCEDURE PROTOCOL

PRE-TREATMENT ACTIVITIES

STUDY QUALIFICATION

SIGNING OF INFORMED CONSENT FORM

The PI will commence by presenting and reviewing in detail the items in the informed consent form with the individual's designated caregiver(s) and answer any questions he or she may have. To proceed, the individual's designated caregiver must willingly sign the informed consent form.

ASSIGNMENT OF SUBJECT IDENTIFICATION NUMBER

The subject will be assigned a unique subject identification number based upon his or her order of entry into the study.

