Following completion of the 4-week Treatment Administration Phase (after completion of all 8 treatment administrations), the following study measures will be recorded:

- Aberrant Behavior Checklist (ABC)
- Clinical Global Impressions (CGI)
- Caregiver Satisfaction with Study Outcome
- Caregiver Perceived Group Allocation and Rationale
- > Administration Investigator Perceived Group Allocation and Rationale

POST-TREATMENT EVALUATION PHASE

WEEK 8: All Subjects

Four weeks following completion of the 4-week Treatment Administration Phase (8 weeks after study onset), the following study measures will be recorded:

- ➤ Aberrant Behavior Checklist (ABC)
- Clinical Global Impressions (CGI)
- Medication and therapy use review
- > Adverse events evaluation
- > Caregiver Satisfaction with Study Outcome
- Caregiver Perceived Group Allocation and Rationale
- Administration Investigator Perceived Group Allocation and Rationale

STATISTICAL ANALYSIS PLAN

The aim of this study is to determine if the treatment effect of the Erchonia® HLS laser device for the active treatment group is greater than that for the placebo treatment group.

The study will be considered a success if, using the Intent-To-Treat (ITT) Last Observation Carried Forward (LOCF) analysis, the primary endpoint is statistically significant at the 0.05 level.

PRIMARY EFFICACY OUTCOME MEASURE

The primary efficacy outcome measure in this study is the mean change from baseline to study endpoint (end of the four-week treatment period) in the Aberrant Behavior Checklist (ABC) Irritability Subscale score.

Study success will be established through the detection of a minimum mean difference of -8.5 points between test and placebo groups in the change in ABC Irritability Subscale score from baseline to study endpoint (end of treatment week 4) adjusted for the baseline ABC Irritability Subscale score. The -8.5-point mean difference between treatment groups is considered clinically relevant with a SD of 8.9, a two-sided test with 80% power and a 5% level of significance.

Null Hypothesis: There is no difference in the mean change in ABC Irritability Subscale score from baseline to study endpoint adjusted for the baseline ABC Irritability Subscale score between active treatment and placebo groups, to the effect of less than -8.5 points.

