For the continuous primary efficacy measure of ABC Irritability Subscale score, change scores will be evaluated by analysis of covariance (ANCOVA). The ANCOVA models for LOCF data sets will include the baseline measure as a covariate and treatment (active of placebo) as main effects.

Secondary Measures Analysis

- ➤ For the continuous secondary efficacy measures of the other 4 ABC Subscale scores, and the Global Score, change scores will be evaluated by analysis of covariance (ANCOVA). The ANCOVA models for LOCF data sets will include the baseline measure as a covariate and treatment (active of placebo) as main effects. A two-way significance level of 5% will be considered statistically significant.
- ➤ The categorical measures of the CGI will be analyzed within the framework of the generalized Cochran-Mantel Haenszel (CMH) procedure.
- Responder rate will be evaluated using Fisher's exact test to compare the proportion of responder rates between the test and control groups.

P-values will be 2-tailed tests of significance rounded to 3 decimal places. All analyses will be performed at the 5% significance level.

CAREGIVER SATISFACTION

Caregiver satisfaction ratings will be descriptively presented through the number and percentage of responses per response category. Fischer's Exact Test will be employed to determine the significance of the difference in categorical responses between treatment groups.

BLINDING EFFICACY EVALUATION

Blinding efficacy evaluation will be conducted through analysis of findings from the Caregiver and the Assessment Investigator Perceived Subject Group Allocation and Rationale responses, recorded at completion of the procedure administration phase (study endpoint).

Statistical evaluation of blinding efficacy will be performed as follows:

- (i) The percentage of caregivers who correctly perceived the subject's procedure group assignment and the percentage of caregivers who did not correctly perceive the subject's procedure group assignment will be calculated.
- (ii) The percentage of times the assessment investigators correctly perceived subjects' procedure group assignment and the percentage of times the assessment investigators did not correctly perceive subjects' procedure group assignment will be calculated.

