- (iii) The **Fischer's Exact categorical analysis technique** for comparison of proportion of successes (accurate procedure group assignment determination) and failures (inaccurate procedure group assignment determination) between subject

- groups will be performed for each of the caregiver and assessment investigator determinations.
- (iv) **Qualitative analysis confirmation:** Evaluation of the comments provided by the caregiver and assessment investigators in the rationale section to explain the guess at group assignment will be evaluated and interpreted as follows to either support or negate the numerical findings:
 - Positive blinding efficacy will be supported through qualitative assessment of comments provided to support perceived group assignment that pertain to the determination being made based on treatment efficacy or lack thereof; e.g.: 'My child has been calmer and communicating better lately, so I think he got the real treatment' or 'I haven't noticed any change in my child's behavior at all, so I believe he got the fake treatment.'
 - Blinding will be determined to have failed if comments provided to support perceived group assignment pertain to factors such as sensation/visual clues, such as 'I saw/didn't see a light go on the laser', or other factors that pertain to blinding having been compromised such as 'I overheard the doctor saying my child was/wasn't getting the real treatment.'

SAFETY ANALYSES

Safety analyses will be completed on all subjects who were randomized to treatment group and received at least the first study treatment administration with the Erchonia® HLS Laser device.

Safety will be assessed by evaluating and comparing frequency and incidence of observed and/or reported adverse events between test and placebo treatment groups. A chi-square test with a continuity correction will be performed to compare the percentage of subjects who had adverse events and/or reactions between the test and placebo group subjects.

SAFETY AND CONFIDENTIALITY ISSUES

ADVERSE EVENTS

At any time throughout the study, any adverse event reported by a subject and/or subject's caregiver and/or observed by the study investigator will be recorded on the case report form and subsequently evaluated by the Principal Investigator for its relation to the study treatment and whether or not any corrective action need be taken. All applicable adverse events will be reported to the IRB and EC, if applicable.

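### The only formal blinding test compares correct-guess rates between arms, so it misses unblinding that is similar in both arms and can flag a mere lean in guessing; the visit schedule also names a different investigator's guess than the SAP analyses

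*Combined protocol and SAP*

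**What the plan says.** The SAP section Blinding Efficacy Evaluation has four items, applied to guesses made at study endpoint (end of Week 4).

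- Items (i) and (ii) report percentages correct and incorrect for caregivers and for assessors. For assessors the quantity is "The percentage of times the assessment investigators correctly perceived subjects' procedure group assignment". No interval or reference value is attached.
- Item (iii) is the only hypothesis test. It is Fisher's exact test "for comparison of proportion of successes (accurate procedure group assignment determination) and failures (inaccurate procedure group assignment determination) between subject" groups, run separately for caregivers and assessment investigators.
- Item (iv) is a qualitative reading of the stated reasons, and it holds the only failure rule: "Blinding will be determined to have failed if comments provided to support perceived group assignment pertain to factors such as sensation/visual clues", or other signs that the blind was compromised. Reasons based on perceived efficacy count in favour of blinding.

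The section Blinding Efficacy Evaluation Tools offers two answers, true or fake device, and names the "Assessment Investigator Perceived Subject Group Allocation and Rationale". The Study Evaluation Timeline, at Week 4 End and again at Week 8, instead lists the "Administration Investigator Perceived Group Allocation and Rationale" beside the caregiver's guess. The two roles differ. Under Double Blind Design, item 3, "Only the administration investigator will be aware of whether a subject is assigned to Treatment Group A or B"; the assessment investigator is not.

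**The concern.** Blinding fails when guesses depend on the treatment actually received. Item (iii) asks something else: whether one arm guesses right more often than the other. When both arms guess right equally often, however often that is, the test has nothing to detect. When everyone leans towards the same answer, the arm for which that answer is correct scores higher, and the test can reject although no one knows anything.

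This matters because the responder endpoint combines the primary caregiver's ABC Irritability rating with the clinician's CGI-I, so its credibility rests partly on the caregiver and assessor blinds. In the earlier controlled trial, 80% of active-procedure subjects "met the Positive Responder Rate compared with no (0%) placebo group subjects", a contrast that invites close scrutiny of blinding.

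The schedule conflict has a different consequence. Caregiver guesses can be re-tabulated at any time, but assessor guesses that were never collected cannot be recovered.

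**Working it through.** **Inputs.** 20 enrolled and 18 evaluable per group (Rationale and Justification for Sample Size); 1:1 allocation; two-tailed 5% level (Statistical Analysis); two answer options (Blinding Efficacy Evaluation Tools). The documents give no guess rates, so those below are assumptions shown over a range.

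**The plan's own figure.** The plan states none for the blinding test. The sample size that sets the table size reproduces: 2 × (1.960 + 0.842)² × (8.9/8.5)² = 17.2, rounded up to 18. Then 18/0.89 = 20.2, which the plan gives as 20.

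**What each table measures.** Let a be the proportion answering 'true' in the active arm and b the proportion answering 'true' in the placebo arm. The proportion correct is a in active and 1 − b in placebo.

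- Item (iii) compares a with 1 − b. The difference is a + b − 1, which is zero when guesses split evenly overall. It measures lean.
- Guess by arm compares a with b. The difference a − b is zero when guesses do not depend on treatment. It measures unblinding.

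**Single tables, Fisher's exact two-sided p, 20 per arm**

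| Situation | Correct, active / placebo | Item (iii) | Guess by arm |
|---|---|---|---|
| Everyone right | 20 / 20 | 1.00 | 1.5e-11 |
| Nearly everyone right | 18 / 18 | 1.00 | 5.3e-7 |
| No information, 12 of 20 say 'true' | 12 / 8 | 0.34 | 1.00 |
| No information, 13 of 20 say 'true' | 13 / 7 | 0.11 | 1.00 |
| No information, 14 of 20 say 'true' | 14 / 6 | 0.026 | 1.00 |

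At 18 per arm, 16 of 18 correct in both arms gives p = 1.00 under item (iii). A 13 / 5 split gives 0.018 and a 12 / 6 split gives 0.094.

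**Rejection rates, exact enumeration of two independent binomials, p ≤ 0.05, 20 per arm**

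| Assumption | Item (iii) | Guess by arm |
|---|---|---|
| Blinding intact, 50% say 'true' in each arm | 2.0% | 2.0% |
| Blinding intact, 60% | 14% | 2.4% |
| Blinding intact, 70% | 60% | 2.5% |
| Blinding intact, 80% | 96% | 2.3% |
| 70% correct in both arms | 2.5% | 60% |
| 80% correct in both arms | 2.3% | 96% |
| 90% correct in both arms | 1.2% | >99.9% |

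At 18 per arm the intact-blinding rates for item (iii) are 3%, 16%, 61% and 96%.

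**Bang's index.** With two answer options it equals 2 × proportion correct − 1 in each arm. 18 of 20 correct gives 0.80 (exact 95% CI 0.37 to 0.98). With 14 of 20 saying 'true' in each arm, it is +0.40 (−0.09 to 0.76) in active and −0.40 (−0.76 to 0.09) in placebo. These opposite signs are the pattern of a lean without unblinding.

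**Limit of any endpoint guess.** Suppose every guess simply follows response at 80% active and 0% placebo. The 80% pools the 21 randomised active subjects with the 19 placebo subjects who crossed over, so it is only an illustration. Then 16 of 20 and 20 of 20 would be correct. Item (iii) gives p = 0.11 and guess by arm gives p = 1.5e-7, with no device cue at all.

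**Schedule.** The tool description and SAP items (ii) to (iv) require the assessment investigator's guess. The Week 4 and Week 8 lists contain only the caregiver's and the administration investigator's. These places cannot all be followed as written.

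**The case against.** Four points can be made for the plan.

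First, nothing depends on the p-value in (iii): the stated failure rule is the comment review, and items (i) and (ii) would show a high percentage correct to any reader. This stands as a limit on the consequence. It also means that the one inferential result offered on blinding can be 1.00 when every guess is right, beside percentages with no interval or reference.

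Second, guess by arm relabels the same four cells. That is true, and it makes the fix cheap. It does not make the planned comparison informative.

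Third, item (iii) does respond to one-sided unblinding: 20 of 20 correct in active and 10 of 20 in placebo gives p = 0.0004 under either test. This also stands. But (iii) reacts only because the one-sided cue produces an overall lean, and it cannot separate that from a lean with no cue.

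Fourth, the replacement is sensitive to visible efficacy, as the last calculation shows, so a significant result would not by itself prove a broken blind. This is correct, and is why the result must be read with item (iv).

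On the schedule, the case report forms in Appendix C were not available for this review and may ask the right person. The loss of assessor guesses is therefore a risk, not an established fact.

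**Conclusion.** The concern holds. Item (iii) has no useful power against unblinding that is similar in both arms: it rejects in 1% to 3% of trials at 70% to 90% correct, about the same as under pure guessing. It can also reject with blinding intact once the common lean is about 70% or more; weaker leans, such as 12 or 13 of 20, are not significant. These results rest on assumed guess rates, two answer options, independent guesses and 20 (or 18) subjects per arm. The conflict over which investigator guesses is a plain contradiction between the schedule and both the tool description and the SAP. Alpha, sample size and the primary ANCOVA are untouched. This should be corrected, but it does not threaten the primary test.

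**What to change.** 1. Replace item (iii) with a table of guess (true or fake) by actual arm, analysed by Fisher's exact test, with Bang's blinding index and 95% CI for each arm. Do this separately for caregivers and assessment investigators.
2. Give the percentages in (i) and (ii) an exact 95% CI and state the chance reference. With equal arms this is 50% whatever the lean, since (q + 1 − q)/2 = 0.5.
3. State that these results are read together with the rationale review in (iv), because guesses at study endpoint also reflect perceived efficacy.
4. Reconcile the Week 4 and Week 8 schedule lines with the tool description and SAP so that the assessment investigator's guess is collected. Week 4 matters most, as it is the time point analysed. The administration investigator's guess can stay as an additional item.

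The cost is SAP wording, two schedule lines and the matching case report form if it follows the schedule. The question asked and the visits stay the same. Item 4 must be settled before data collection; the analysis wording should be fixed before unblinding.

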- 1. **IRC# 05122, NSR# DER-001:** Erchonia® EML Breast Implant Clinical Study; Version 2, 08/10/05.
- IRC# 02093, NSR# DTU-003: Erchonia® EML Liposuction Clinical Study; Version 2. 08/12/2003.

PLACEBO DEVICE INFORMATION

The placebo (fake) Erchonia® HLS to be employed in this pivotal trial is designed to have the same physical appearance as the actual Erchonia® HLS, including the appearance of any visible light output. The placebo laser device will therefore emit light when activated that is indistinguishable to both the subject and to the investigator. As the laser light does not put out any notable degree of heat or noise, these are not distinguishing factors for subjects or investigators between the active and placebo treatment groups.

The design of the placebo device to be employed in this pivotal trial is identical to that employed in numerous prior feasibility and pivotal clinical trials employing Erchonia Corporation low level laser devices. In each of those prior studies, the lack of effectiveness of the placebo device on the target indication was clearly established. The results from several of these placebo-controlled pivotal studies conducted to evaluate efficacy of the actual Erchonia laser device over a placebo device, with the placebo device configured in the manner described and intended in the current pivotal trial, were used to support 510(k) submissions to the Food and Drug Administration (FDA) that resulted in clearances being granted for various indications. In each of these pivotal trials, the active device comprised red light laser diodes as in the current study, with the placebo device designed to emit the same visible light output without therapeutic effect.

Application of the same placebo device design and configuration in numerous prior pivotal trials whose results demonstrated statistical significance of application of the active laser device over a placebo device and resulted in FDA clearances establishes the lack of effectiveness of the placebo device with respect to the placebo device design intended for application in the current pivotal trial.

Please find below a listing of each of the FDA 510(k) clearances pertaining to the family of Erchonia® red diode laser devices:

> **510(k)#**: K121695 & K082609

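### Blinding step (iv) declares failure from what a comment is about, not from whether the cue revealed the arm, so a caregiver convinced by the sham's light counts as failed blinding

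*Combined protocol and SAP*

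**What the plan says.** The evaluation is in the SAP under Blinding Efficacy Evaluation and has four steps.

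- Steps (i) and (ii) are descriptive. For caregivers the plan reports "The percentage of caregivers who correctly perceived the subject's procedure group assignment" and its complement, and it does the same for the assessment investigators. No level is named at which blinding passes or fails.
- Step (iii) is a Fisher exact test for "comparison of proportion of successes (accurate procedure group assignment determination) and failures (inaccurate procedure group assignment determination) between subject" groups, run for each type of rater.
- Step (iv) reads the free-text reasons given "to explain the guess at group assignment will be evaluated and interpreted as follows to either support or negate the numerical findings". Reasons based on perceived benefit, or its absence, support blinding. For the rest, "Blinding will be determined to have failed if comments provided to support perceived group assignment pertain to factors such as sensation/visual clues", with the example "such as 'I saw/didn't see a light go on the laser". A second example is overhearing staff reveal the assignment.

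The device sections describe the sham. Placebo Device Information states: "The placebo laser device will therefore emit light when activated that is indistinguishable to both the subject and to the investigator". Double Blind Design, item 2, concludes that "there are no distinguishing factors between the active and placebo lasers for subjects or investigators".

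**The concern.** A cue threatens blinding only if it differs between arms and so lets the rater work out the assignment. Step (iv) asks a different question: what the comment is about. It does not ask which arm the child was in, whether the guess was right, or whether the two devices differ in the cue cited.

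If the sham works as described, light is visible in both arms. A caregiver of a placebo child who reasons from the light to the active device has been deceived as intended, and the rule counts that as a failure. A caregiver who saw a real difference between devices and guessed correctly gets the same verdict. Because step (iv) can negate the numerical steps, a favourable count of guesses does not protect against a wrong verdict.

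At stake is the credibility of the blinding statement. The SAP specifies the primary caregiver's rating for the ABC Irritability component of the responder definition and for the other four ABC subscales, and the caregiver is also the person whose guess is collected. The statement on caregiver blinding therefore bears directly on how those outcomes are read.

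**Working it through.** **Inputs.** From the protocol, Subject Sample Size: 40 children, 20 per arm, hence up to 40 caregiver guesses at study endpoint. From the SAP: steps (i) to (iv) as above. Not in the documents: how often caregivers will cite a light or sensation. This is assumed at 1% to 5% per caregiver, with caregivers independent. The plan states no figure of its own for blinding, so there is none to reproduce.

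**1. Two extreme cases, 20 caregivers per arm.**

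| | (a) Light seen in both arms, all guess active | (b) A cue reveals the arm to everyone |
|---|---|---|
| Correct, active arm | 20/20 | 20/20 |
| Correct, placebo arm | 0/20 | 20/20 |
| Correct overall | 20/40 = 50% | 40/40 = 100% |
| Per-arm index, 2 × proportion correct − 1 | +1.0 and −1.0 | +1.0 and +1.0 |
| Step (iii), Fisher exact p | 1.5e-11 | 1.0 |
| Step (iv) | failed | failed |

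In (a) the guesses carry no information on allocation. In (b) they carry all of it. Step (iv) does not separate the two cases.

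**2. Why step (iii) does not repair this.** It tests whether accuracy differs between arms, not whether accuracy exceeds chance. Suppose a fraction g of raters guess active whatever the arm. The proportion correct is g in the active arm and 1 − g in the placebo arm. With equal arms the overall proportion is (g + 1 − g)/2 = 50% for any g. Yet the arms differ in accuracy whenever g is not one half. With g = 0.75 the counts are 15/20 and 5/20, which is 50% correct overall, and Fisher p = 0.004. The test responds to a shared leaning towards one answer and is silent when everyone is right. The overall percentage correct does separate (a) from (b), but the plan attaches no decision to it.

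**3. The missing number of comments.** If one cue comment were enough, the chance of at least one among 40 caregivers is 1 − (1 − p)^40:

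- p = 1%: 1 − 0.99^40 = 33%
- p = 2%: 1 − 0.98^40 = 55%
- p = 5%: 1 − 0.95^40 = 87%

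These figures depend on the assumed rates and on the one-comment reading. The result in items 1 and 2 depends on neither.

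**The case against.** Several points on the other side have weight.

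- *Step (iv) is one part of a larger evaluation.* It is labelled as qualitative confirmation, and steps (i) to (iii) do use correctness and group. A reader might infer that the whole blinding evaluation ignores both; the documents do not support that. What remains is that the earlier steps have no pass mark and step (iv) may negate them.
- *The text says comments, in the plural.* A reader might infer that a single remark settles the verdict. The wording permits that but does not state it. The supportable criticism is that no number or proportion is given. The trigger probabilities are conditional on the stronger reading, and on comments being the stated reason for a guess rather than a passing mention.
- *The identical light output is a design claim that the blinding check exists to test.* This is fair, and a remark about not seeing a light could be informative. The documents also do not say whether caregivers attend treatments. But a check of that claim has to compare cue reports and guesses between arms, which step (iv) does not do.
- *Treating cue comments as a warning is conservative.* As a warning, yes. As a verdict, it condemns a working sham and a broken one alike.
- *Overheard disclosure is a true breach.* This stands. The fault is in placing uninformative device cues in the same class.

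One might also double the number of comments by adding an investigator's guess for each child. That is not supported. The Blinding Efficacy Evaluation Tools and the SAP name the assessment investigator, while the Study Evaluation Timeline schedules the guess for the administration investigator. One person may supply many of those guesses, so independence could not be assumed.

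**Conclusion.** The concern holds for step (iv). As worded, the rule gives a wrong result in a case that the plan's own sham design makes likely: a placebo caregiver persuaded by the light. It returns one verdict for two situations as far apart as 50% and 100% correct guesses, and step (iii) points the wrong way in both (p of about 1e-11 and p = 1.0). This conclusion uses only the planned 20 per arm and the logic of the rule; the two cases are deliberate extremes. The 33% to 87% range is illustrative and rests on assumed comment rates, independent caregivers and one comment sufficing.

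A reader might infer that a failed blinding verdict would undo the efficacy result. The documents do not say so: study success depends on the ITT-LOCF primary analysis, and no consequence is attached to step (iv). The harm is confined to the blinding conclusion, which matters for interpreting caregiver-rated ABC outcomes. The point should be corrected before unblinding; it is not a flaw in the primary test.

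**What to change.** Rewrite step (iv) as follows.

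1. Before unblinding, existing staff without access to arm, including the A/B label, code each verbatim rationale as efficacy, device cue, disclosure or none.
2. After unblinding, tabulate guesses by rationale, actual arm and correctness, separately for caregivers and for the assessment investigator. Align the Study Evaluation Timeline with the SAP on which investigator is asked.
3. Treat device-cue comments as evidence of compromised blinding only when cue-based guesses track actual assignment. That means an overall proportion correct above 50%, reported with an exact confidence interval and with the proportions in each arm. Mention of a cue alone is not enough.
4. Report any documented disclosure as a breach in its own right.

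Two additions should be avoided. A binomial significance test should not be the sole gate. At the 5% level one-sided it needs at least five cue-based guesses, all correct (0.5^5 = 0.031; four give 0.5^4 = 0.0625). Five or more cue comments among 40 caregivers would arise with probability of about 0.1% at a 2% comment rate and 5% at a 5% rate. Nor should correct guessers be dropped from the ANCOVA. That selects on a post-randomisation variable, and in case (a) it would remove all 20 active children and no placebo children although the sham is intact.

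The cost is revised SAP wording, a short coding exercise and one table, from rationales already being collected. The downside is that with few cue comments the result will be descriptive and may be inconclusive.
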